### **4.3 Data Quality**

Monitoring and auditing procedures defined/agreed by the sponsor will be followed in compliance with current GCP guidelines. Each center will be visited at regular intervals by a monitor to ensure compliance with the study protocol, GCP guideline, and other regulatory aspects. This will include on-site review of the eCRF for completeness and clarity, consistency with source documents, and clarification of administrative matters.

### **4.4 Documentation**

Entries made in the eCRF must be either verifiable against source documents or have been directly entered into the eCRF, in which case the entry in the eCRF will be considered as the source data. The source data parameter to be verified and the identification of the source document must be

documented. The study file and all source data should be retained/archived until notification by the sponsor for change of archive site or destruction.

## **5. ETHICAL AND LEGAL ASPECTS**

### **5.1 Institutional Review Board (IRB)**

Documented approval from the IRB will be obtained for all participating trial center(s)/clinic(s) prior to study start, according to GCP and applicable laws and regulations. When necessary, an extension, amendment, or renewal of the IRB approval must be obtained and also forwarded to the sponsor. The IRB must supply to the sponsor, upon request, a list of the IRB members involved in the vote and a statement to confirm that the IRB is organized and operates according to GCP and applicable laws and regulations.

### **5.2 Ethical Conduct of the Study**

The procedures set out in this protocol, pertaining to the conduct, evaluation, and documentation of this study, are designed to ensure that the sponsor and investigator abide by GCP guidelines and under the guiding principles detailed in the Declaration of Helsinki. The study will also be carried out in keeping with applicable local laws and regulations. This may include an inspection by the sponsor representatives and/or Regulatory Authority representatives at any time. The investigator must agree to the inspection of study-related records by the Regulatory Authority/sponsor representatives, and must allow direct access to source documents to the Regulatory Authority/sponsor representatives.

Modifications to the study protocol will be implemented by the investigator only after sponsor's approval. However, the investigator may implement a deviation form, or change of the protocol to eliminate any immediate hazard(s) to the trial subjects without prior IRB/sponsor approval. The implemented deviation or change, the reasons for it and, if appropriate, the proposed amendment should be submitted to the IRB/sponsor as soon as possible. Any deviations from the protocol must be fully explained and documented by the investigator.

### **5.3 Regulatory Authority Approvals/Authorizations**

Regulatory Authority approvals/authorizations/notifications, where required, will be in place and fully documented prior to the study's start.

### **5.4 Subject Information Consent**

A core information and Informed Consent Form will be provided. Prior to the beginning of the study, the investigator must have the IRB written approval of the Informed Consent Form and any

other written information that will be provided to the subjects. The written approval of the IRB with the approved Informed Consent Form must be in the study files.

Written informed consent must be obtained before any study specific procedure takes place. Participation in the study and date of informed consent given by the subject should be documented appropriately in the subject's files.

## **5.5 Insurance**

All subjects participating in the study will have insurance coverage by the sponsor, which is in line with applicable laws and/or regulations.

## **5.6 Confidentiality**

All records identifying the subject will be kept confidential and, to the extent permitted by the applicable laws and/or regulations, will not be made publicly available.

Subject names will not be supplied to the sponsor. Only the subject number and subject initials will be recorded in the eCRF, and if the subject name appears on any other document (e.g. pathologist report), it must be obliterated before a copy of the document is supplied to the sponsor. Study findings stored on a computer will be stored in accordance with local data protection laws. The subjects will be informed in writing that representatives of the sponsor, IRB, or Regulatory Authorities may inspect their medical records to verify the information collected, and that all personal information made available for inspection will be handled in strictest confidence and in accordance with local data protection laws.

Even if the results of the study are published, the subject's identity will remain confidential. The investigator will maintain a list to enable subjects' records to be identified.

## 6. STATISTICAL METHODS AND DETERMINATION OF SAMPLE SIZE

### 6.1 Statistical and Analytical Plans

#### 6.1.1 Analytical Populations

##### 6.1.1.1 Intent-to-Treat Population

An intent-to-treat (ITT) population will include subjects who received the intra-articular injection and have at least post-injection efficacy measurements. This cohort will be evaluated for all efficacy variables.

##### 6.1.1.2 Per-Protocol Population

All subjects valid for ITT who completed Visit 6 (Month 6) will be ‘valid per protocol’ (also called ‘valid for efficacy’). Additional criteria may be added prior to unblinding the study database. As with the ITT population, this per-protocol (PP) cohort will also be evaluated for all efficacy variables.

##### 6.1.1.3 Safety Population

Any subject who was randomized and completed Visit 2 (Week -5) will be included in the evaluation of safety. This cohort will be evaluated for all safety variables.

#### 6.1.2 Treatment Group Comparability

Demographic variables, medical history, treatment duration, and efficacy variables at baseline will be summarized by treatment group for the subjects valid for potential safety analysis. Because, in theory, the goal of randomization is to balance out the patient characteristics, statistical tests are not planned for these variables.

#### 6.1.3 Significance Level

The primary efficacy hypothesis tests will be performed using a 5% significance level (but, for the MRI improvement evaluation, it shall meet the validity criteria). For the secondary efficacy endpoints, hypothesis tests will be performed individually at the 5% significance level. All hypothesis tests except for the primary efficacy hypothesis tests will be performed with two-sided alternative hypotheses.

#### 6.1.4 Primary Efficacy Analyses

For primary efficacy endpoints, the joint functional improvement of knee joint will be evaluated using the following three co-primary efficacy variables and gatekeeping procedures will be used for these three hypothesis tests.

Three hypothesis tests will be performed in the following order: 1) Change of WOMAC score within study group, 2) Change of VAS score within study group and 3) MRI improvement evaluation in the study group. If null hypothesis is dismissed at 5% significance level for the first hypothesis test, the second hypothesis will also be tested at 5% significance level. Then, for MRI improvement evaluation, the test will be performed to confirm if the percentage of subjects whose final PI evaluation is ‘improvement’ meets the validity criteria. If null hypothesis is not dismissed at 5% significance level or it is lower than the validity criteria, the hypothesis test is stopped and it is concluded only previous item of which null hypothesis is dismissed is significant.

##### 1) Change of WOMAC score from baseline at Month 6 (JointStem group)

Change of WOMAC score from baseline at Month 6 will be tested using paired t-test (one-sided test,  $\alpha=0.05$ ) with the null hypothesis equal to zero. If change of WOMAC score from baseline at Month 6 doesn't satisfy normal distribution, Wilcoxon signed rank test will be performed.

If null hypothesis is dismissed, the conclusion that the function of knee joint is improved from at least subjects who administer IP can be drawn.

##### 2) Change of VAS score from baseline at Month 6 (JointStem group)

Change of VAS score from baseline at Month 6 will be tested using paired t-test (one-sided test,  $\alpha=0.05$ ) with the null hypothesis equal to zero. If change of VAS score from baseline at Month 6 doesn't satisfy normal distribution, Wilcoxon signed rank test will be performed.

If null hypothesis is dismissed, the conclusion that the pain of degenerative arthritis is reduced from at least subjects who administer IP can be drawn.

##### 3) MRI improvement evaluation at Month 6 (JointStem group)

MRI improvement evaluation will be finally analyzed through the following two steps:

- Radiologist will compare and analyze MRI results before and after the administration of IP and write a report for each subject.
- Principal Investigator will evaluate MRI results of subjects as one of three conditions (a: improvement, b: no change, c: progress) based on the radiologist's report stated above.

→ The frequency and percentage of subjects whose final PI evaluation is 'improvement' will be calculated per group.

If the percentage of subjects whose final PI evaluation is at least 36%, the conclusion that the damaged cartilage of knee joint is improved in the subjects who administer JointStem can be drawn.

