## Protocol Synopsis

**Title:** A Phase 2, Double-Blind, Randomized, Controlled Study to Evaluate the Efficacy and Safety of JointStem, Autologous Adipose Tissue Derived Mesenchymal Stem Cells, in Treatment of Osteoarthritis

**Phase:** Phase 2

**Indication:** Osteoarthritis (Degenerative Arthritis)

**Study Objective:** To evaluate the efficacy and safety of autologous adipose tissue derived mesenchymal stem cells (AdMSC) for the treatment of osteoarthritis

**Study Design:** This study is a double-blind, randomized, controlled study with two arms to evaluate JointStem as a treatment for subjects with osteoarthritis. Following a 2-week screening period, approximately 30 subjects will be randomly assigned into one of the following two arms in a 2:1 ratio (2 JointStem : 1 positive control):

- JointStem (1x10^8 cells/3mL)
- Positive control: Synvisc-One®

After each subject completes 6-month visit (Visit 6) and the data management team confirms all individual data have no issue, the individual database will be locked and the blinding will be open for the statistical analysis. Only subjects who are randomized to JointStem group will then be scheduled for 9-month and 12-month follow-up visits (Visits 7 and 8).

Long-term follow-up visit will be conducted to collect long-term feedbacks (records of medications and treatments) following 2 years after injection for all subjects who complete 6-month visit and accept the long-term follow-up visit.

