**Statistical Analysis:**

1. Co-primary Endpoints

Using the following three co-primary efficacy variables, the joint functional improvement of knee joint will be evaluated and gatekeeping procedures will be used for these three hypothesis tests.

- 1) Change of WOMAC score from baseline at Month 6 (JointStem group)  
It will be tested using paired t-test (one-sided test,  $\alpha=0.05$ ). If change of WOMAC score from baseline at Month 6 doesn't satisfy normal distribution, Wilcoxon signed rank test will be performed.
- 2) Change of VAS score from baseline at Month 6 (JointStem group)  
It will be tested using paired t-test (one-sided test,  $\alpha=0.05$ ). If change of VAS score from baseline at Month 6 doesn't satisfy normal distribution, Wilcoxon signed rank test will be performed.
- 3) MRI improvement evaluation at Month 6 (JointStem group)  
The frequency and percentage of subjects whose final PI evaluation is 'improvement' will be calculated (validity criteria: 36%).

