## **3.6 Study Endpoints and Variables**

### **3.6.1 Study Endpoints**

The co-primary endpoints are:

Using the following three co-primary efficacy variables, the joint functional improvement of knee joint will be evaluated and gatekeeping procedures will be used for these three hypothesis tests.

- 1) Change of WOMAC score from baseline at Month 6 (JointStem group)
- 2) Change of VAS score from baseline at Month 6 (JointStem group)
- 3) MRI improvement evaluation at Month 6 (JointStem group)

MRI improvement evaluation will be finally analyzed through the following two steps:

- Radiologist will compare and analyze MRI results before and after the administration of IP and write a report for each subject.
- Principal Investigator will evaluate MRI results of subjects as one of three conditions (a: improvement, b: no change, c: progress) based on the radiologist's report stated above.

The secondary endpoints are:

- 1) JointStem group vs. positive control group
  - ① Change of WOMAC score from baseline at Month 6
  - ② Change of VAS score from baseline at Month 6
  - ③ Change of KOOS from baseline at Month 6
  - ④ Change of Lysholm Knee Scoring Scale from baseline at Month 6
  - ⑤ Change of IKDC from baseline at Month 6
  - ⑥ Change of RAND-36 Score from baseline at Month 6
- 2) JointStem group
  - ① Change of WOMAC score from baseline at Months 9 and 12
  - ② Change of VAS score from baseline at Months 9 and 12
  - ③ Comparison of MRI improvement evaluations between at Month 6 and at Months 12
  - ④ Change of Lysholm Knee Scoring Scale from baseline at Months 6, 9 and 12
  - ⑤ Change of KOOS from baseline at Months 6, 9 and 12
  - ⑥ Change of IKDC from baseline at Months 6, 9 and 12
  - ⑦ Change of RAND-36 Score from baseline at Months 6, 9 and 12
- 3) Incidence of adverse events and laboratory abnormalities

Exploratory Endpoint is:

All efficacy variables and the history of treatments and medications, which are measured at a long-term follow-up visit (24 months after injection) will be analyzed between treatment groups to see any long-term effects of JointStem. Also, MRI results of long-term follow-up visit will be compared to previous MRI results to see any long-term effects of JointStem.

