## **6.2 Determination of Sample Size**

There was no formal sample size calculation since this is a proof-of-concept study and is not a hypothesis-driven study. The number of enrolled subjects is predefined at n=30, for 20 subjects per study group and 10 subjects per control group.

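### The 36% MRI rule gives progress no role, so it can support a conclusion that cartilage is improved when more JointStem subjects worsened than improved

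*Protocol*

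**What the plan says.** In Protocol 6.1.4, item 3, a radiologist reports on the scans before and after injection. From that report, "Principal Investigator will evaluate MRI results of subjects as one of three conditions (a: improvement, b: no change, c: progress"). Section 3.6.1 and the SAP (1.2.1 and 6.1) use the same three categories.

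The decision uses one category. Protocol 6.1.4 says the test is to "confirm if the percentage of subjects whose final PI evaluation is ‘improvement’ meets the validity criteria", and the synopsis sets that criterion at 36%. The conclusion follows in item 3: "If the percentage of subjects whose final PI evaluation is at least 36%, the conclusion that the damaged cartilage of knee joint is improved" can be drawn for JointStem subjects. That sentence leaves out the category name, but the line before it, the synopsis and the opening of 6.1.4 make clear that improvement is meant. SAP 6.1 repeats the rule.

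Protocol 6.1.3 exempts MRI from the 5% significance level; it need only meet the criterion. MRI comes third in the gatekeeping order, after the within-group WOMAC and VAS tests. Progress is counted only in SAP 6.2.3, a secondary analysis that tabulates all three categories at Months 6 and 12 and applies Bowker's test between those visits.

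On size, "The number of enrolled subjects is predefined at n=30, for 20 subjects per study group and 10 subjects per control group".

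**The concern.** WOMAC and VAS are tested on change from baseline, so a subject who gets worse counts against one who gets better. MRI is the only co-primary where worsening costs nothing: a subject rated progress is treated exactly like one rated no change. It is also the only structural claim in the primary family, and its conclusion is about the state of the cartilage in the treated group, not about the number of responders.

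A 36% pass leaves up to 64% of subjects who may have progressed. The third co-primary can therefore succeed, with a stated conclusion of improvement, on data in which worsening predominates.

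**Working it through.** **Inputs from the documents.** Threshold: at least 36% rated improvement (Protocol synopsis and 6.1.4; SAP 6.1). JointStem subjects: 20 (Protocol 6.2; consistent with 2:1 allocation, 30 × 2/3 = 20). The 36% has no stated derivation, reference rate or error rate, so there is no plan figure to reproduce beyond the 20/10 split.

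**Step 1: the rule in counts.** 7/20 = 35.0% fails; 8/20 = 40.0% passes. The rule is 8 or more improved.

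**Step 2: passing results with more progressed than improved.**
- 8 improved leaves 12 others; 9, 10, 11 or 12 of them may have progressed.
- 9 improved leaves 11; 10 or 11 may have progressed.
- 10 or more improved leaves at most 10, so progress cannot exceed improvement.

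Fewer evaluable scans do not remove the problem:

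| Evaluable n | Improved needed | Most who can have progressed |
|---|---|---|
| 19 | 7 | 12 |
| 18 | 7 | 11 |
| 17 | 7 | 10 |
| 16 | 6 | 10 |
| 15 | 6 | 9 |

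**Step 3: how often.** The documents give no true rates, so all rates below are assumptions. With i improved, w progressed, independent subjects and n = 20,

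P(i, w) = 20! / [i! w! (20 − i − w)!] × pI^i × pP^w × pN^(20 − i − w).

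The chance of a contradictory pass is the sum over the six results in step 2. The chance that the rule passes is P(X ≥ 8) for X binomial(20, pI).

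| Assumed improved / progressed | Rule passes | Passes with progressed > improved | Share of passes |
|---|---|---|---|
| 36% / 20% | 43.6% | 0.04% | 0.1% |
| 30% / 30% | 22.8% | 0.3% | 1.3% |
| 40% / 40% | 58.4% | 8.3% | 14.1% |
| 36% / 50% | 43.6% | 15.9% | 36.4% |
| 40% / 50% | 58.4% | 22.6% | 38.7% |

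The rule-passes column depends on pI alone: it is 43.6% whether 20% or 50% progress. It therefore does not measure this defect; the next column does.

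**Step 4: effect of also requiring more improved than progressed.** This blocks the six contradictory results and the ties 8–8, 9–9 and 10–10. For example, at 50/30/20 (improved/no change/progress) 86.8% loses 0.2 points to contradictory results and 0.6 to ties, giving 86.1% from unrounded values. The last column instead adds an exact one-sided 5% sign test of improved against progressed.

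| Improved / no change / progress | Rule as written | With added condition | With sign test |
|---|---|---|---|
| 60/30/10 | 97.9% | 97.9% | 85.3% |
| 50/30/20 | 86.8% | 86.1% | 39.5% |
| 30/40/30 | 22.8% | 21.7% | 2.6% |
| 40/10/50 | 58.4% | 27.6% | 1.1% |

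The sign test is demanding at this size: 8 against 1 gives p = 0.0195, but 8 against 2 gives p = 0.055.

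**The case against.** The strongest reply has four parts.

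**A responder proportion is a legitimate endpoint.** The endpoint is named for improvement, and net change would be a different estimand. That is fair as far as it goes. But the conclusion drawn is that the damaged cartilage is improved, which says more than that a given share responded.

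**There are safeguards.** MRI is reached only after WOMAC and VAS succeed, the wording permits the conclusion without compelling it, and SAP 6.2.3 would show an 8-against-12 result. All true, so a reader should not infer that worsening would be hidden. But the gate rests on symptom scores, and the table neither compares improved with progressed nor affects the co-primary decision.

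**This is a small exploratory study.** Protocol 6.2 states: "There was no formal sample size calculation since this is a proof-of-concept study and is not a hypothesis-driven study". That argues against adding a demanding test. It does not justify a prespecified conclusion that its own data can contradict.

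**The contradiction may be rare.** This stands. It is negligible at about 20% progression and becomes material only when progression is high.

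A reader might also take the rule's pass rates with no net change (22.8% at 30/40/30, 58.4% at 40/20/40) as the size of this problem. They are not: the same figures arise if nobody progresses. They reflect a bare cutoff with no reference rate or test, which is a separate matter.

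**Conclusion.** The concern holds as a gap in the decision rule. At n = 20, six passing combinations have more subjects worsened than improved, and nothing in either document stops the conclusion of improved cartilage in those cases. This part is arithmetic and needs no assumption beyond the planned 20 evaluable subjects; it persists at 15 to 19.

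How likely it is depends on rates the documents do not give. Over the assumed cases the chance of a contradictory pass runs from 0.04% (36% improved, 20% progressed) to 22.6% (40% improved, 50% progressed), before allowing for the WOMAC and VAS gate. The documents do not support saying that a contradictory conclusion is probable. The case for correction is that the rule can give a wrong conclusion on the only structural endpoint in the primary family, and that closing the gap is cheap.

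**What to change.** In Protocol 6.1.4 and SAP 6.1, allow the MRI conclusion only if at least 36% of JointStem subjects are rated improvement **and** more subjects are rated improvement than progress. Report Month 6 improved minus progressed, with an exact interval, beside the 36% figure. State the same condition in the synopsis.

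Cost: one sentence in each place and no new data, since the evaluation form in Protocol Appendix 9 already records all three ratings. The loss of pass chance when the product works is very small: none to one decimal place at 60/30/10, and 86.8% to 86.1% at 50/30/20.

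Limit: this removes the self-contradiction but does not control reading variation that scatters ratings both ways (22.8% to 21.7% at 30/40/30). A one-sided sign test of improved against progressed would control that noise, but it cuts the pass chance to 39.5% at 50/30/20, a true net gain of 30 points. It is an option for the sponsor to weigh, not part of the required change.

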**Secondary Endpoints:**  
1) JointStem group vs. positive control group  
① Change of WOMAC score from baseline at Month 6  
② Change of VAS score from baseline at Month 6  
③ Change of KOOS from baseline at Month 6  
④ Change of Lysholm Knee Scoring Scale from baseline at Month 6  
⑤ Change of IKDC from baseline at Month 6  
⑥ Change of RAND-36 Score from baseline at Month 6  
2) JointStem group  
① Change of WOMAC score from baseline at Months 9 and 12  
② Change of VAS score from baseline at Months 9 and 12  
③ Comparison of MRI improvement evaluations between at Month 6 and at Month 12  
④ Change of Lysholm Knee Scoring Scale from baseline at Months 6, 9 and 12  
⑤ Change of KOOS from baseline at Months 6, 9 and 12

- ⑥ Change of IKDC from baseline at Months 6, 9 and 12
- ⑦ Change of RAND-36 Score from baseline at Months 6, 9 and 12
- 3) Incidence of adverse events and laboratory abnormalities

**Exploratory Endpoints:** Analysis of all efficacy scales and MRI results and the history of treatments and medications following 2 years after injection for all subjects who are injected and complete 6-month follow-up visit

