6. EFFICACY ANALYSES

All efficacy analyses will be performed on the ITT and PP populations.

The primary efficacy hypothesis tests will be performed using a 5% significance level (but, for the MRI improvement evaluation, it shall meet the effective judgment criteria). For the secondary efficacy endpoints, hypothesis tests will be performed individually at the 5% significance level. All hypothesis tests except for the primary efficacy hypothesis tests will be performed with two-sided alternative hypotheses.

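### After WOMAC and VAS pass, the Month 6 MRI step concludes that cartilage is improved from an observed 36%, with no null rate, interval or error rate, and MRI alone among the co-primary variables has no planned Month 6 between-arm difference

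*Protocol*

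**What the plan says.** Protocol 6.1.4 lists three co-primary variables in the JointStem group and states that "gatekeeping procedures will be used for these three hypothesis tests". SAP 1.2.1 and 6.1 say the same. The order is WOMAC, VAS, MRI, and a failure at any step stops the sequence. WOMAC and VAS each have a null of zero change and a one-sided 5% test.

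For MRI, the principal investigator rates each subject as improvement, no change or progress from the radiologist's report. The frequency and percentage rated as improvement "will be calculated per group". If the percentage "is at least 36%, the conclusion that the damaged cartilage of knee joint is improved in the subjects who administer JointStem can be drawn". SAP 6.1 has the same rule.

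MRI is openly exempted from the 5% level: Protocol 6.1.3 says "but, for the MRI improvement evaluation, it shall meet the validity criteria", and SAP section 6 says "but, for the MRI improvement evaluation, it shall meet the effective judgment criteria". The synopsis gives the figure only as "validity criteria: 36" per cent. SAP section 6 adds: "All efficacy analyses will be performed on the ITT and PP populations".

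WOMAC and VAS each also have a secondary Month 6 ANCOVA of JointStem against control, with a difference, 95% CI and p-value (Protocol 6.1.5, SAP 6.2.1 and 6.2.2). MRI is missing from the between-arm lists in the synopsis, Protocol 3.6.1 and SAP 1.2.2. Its only secondary entry is within JointStem: "Comparison of MRI improvement evaluations between at Month 6 and at Month 12". Control subjects do attend Visit 6 (Protocol 3.5.8), and the Schedule of Assessments and Protocol 4.2.6 schedule MRI at that visit for both arms.

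**The concern.** A step presented as a hypothesis test leads to a firm statement about cartilage, but it is a comparison of a point estimate with a fixed number. The reader of the results could not say how often the statement would be made in error, because the plan supplies nothing to compute that from. At the pass mark the data are compatible with a true rate well below 36%.

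The second gap is the comparison with control. MRI ratings are investigator judgements, and some knees may be rated improved in either arm. The control percentage will be in the table, but without a planned difference and interval there is no stated measure of whether JointStem did better. The risk is a co-primary cartilage claim that is read as a JointStem effect when control knees were rated improved just as often.

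**Working it through.** **Inputs.** Threshold 36% (Protocol 6.1.4; SAP 6.1). Planned size 20 JointStem and 10 control (Protocol 6.2; SAP 1.3.3). The documents give no background rate for an improvement rating, so every true or null rate below is an assumption. The 36% itself cannot be reproduced, because no null, target, alpha, power or source is stated for it.

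**The rule as a count.** 0.36 × 20 = 7.2, so at least 8 of 20 (40%) are needed; exactly 36% cannot occur with 20 subjects.

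**Precision at the pass mark.** The exact (Clopper-Pearson) 95% CI for 8/20 is 19.1% to 63.9%. The one-sided 95% lower bound is 21.7%.

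**How often the MRI step passes, taken alone.** P(X ≥ 8), X ~ Binomial(20, p):

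| Assumed true rate p | P(step passes) |
|---|---|
| 10% | 0.0004 |
| 15% | 0.006 |
| 20% | 0.032 |
| 25% | 0.102 |
| 30% | 0.228 |
| 36% | 0.436 |

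Solving P(X ≥ 8) = 0.05 gives p = 21.7%. The cut therefore controls one-sided error at 5% for any null rate up to about 21.7%, and not above it. Because the step is reached only after WOMAC and VAS have rejected, the unconditional chance of making the cartilage statement cannot exceed these values.

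**What a stated null would require.** Smallest count at n = 20 for an exact one-sided 5% binomial test, with attained alpha:

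| Null rate | Count needed | Alpha |
|---|---|---|
| 10% | 5/20 | 0.043 |
| 15% | 7/20 | 0.022 |
| 20% | 8/20 | 0.032 |
| 25% | 9/20 | 0.041 |
| 30% | 10/20 | 0.048 |
| 36% | 12/20 | 0.025 |

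Depending on the null, the present cut is stricter than needed, about right, or up to four responders short.

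**Denominator.** 7/20 = 35.0% fails and 7/19 = 36.8% passes, so ITT and PP could disagree. This is a possible case, not a predicted one: LOCF and the early-termination MRI affect who is counted.

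**Between-arm illustrations.** JointStem minus control with 8/20 in JointStem, exact unconditional 95% CI (score statistic):

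| Control | Difference | 95% CI | Width |
|---|---|---|---|
| 4/10 | 0 points | −38 to +35 | 73 |
| 2/10 | +20 points | −19 to +50 | 69 |
| 1/10 | +30 points | −6 to +56 | 62 |

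All three rows meet the MRI criterion. If both arms share a true rate of 25%, 30% or 36%, the control percentage equals or exceeds the JointStem percentage in 16%, 24% and 34% of the trials that meet it.

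**The case against.** The plan calls itself proof-of-concept and not hypothesis-driven, does not hide that MRI is exempt from the 5% level, and uses a fixed threshold, which is a recognisable choice in a small trial. That stands as far as it goes: it explains the lack of a power calculation. It does not explain why the step is called a hypothesis test or why a firm conclusion follows from it.

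Several stronger readings are tempting and are not supported:

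- *The cartilage claim needs only an observed 36%.* No. WOMAC and VAS must both reject first. Because MRI is last, the WOMAC and VAS error rates are also unaffected.
- *The false-positive rate is 44%.* Only if 36% is the null. If 36% is the target, the same 44% is power. The documents do not say which. Likewise, 12/20 is required only if 36% is the null.
- *The rule is loose whatever the null.* No. For nulls up to about 21.7% it is within 5%, and the documents do not exclude such rates.
- *Only MRI lacks a link to control.* All three co-primary conclusions are drawn within JointStem, and the WOMAC and VAS ANCOVAs gate nothing. What is particular to MRI is the absence of a planned difference with an interval. The unnamed deciding set, ITT or PP, is likewise shared by all three.
- *No control figure will be seen.* It will be tabulated, so a reader can subtract; the interval is what is missing.
- *Equal arms would show JointStem to be inert.* No. The control is active, so equal arms would mean only that the rating cannot be credited to JointStem over its control.

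**Conclusion.** The point holds in this limited form and should be fixed. With WOMAC and VAS passed, the plan permits the statement that cartilage is improved on the strength of 8/20, a result whose exact 95% CI runs from 19% to 64%, without any stated null or error rate. Whether that is adequate depends on a background rate the documents do not give: one-sided 5% error is held up to about 21.7% and exceeded above it, reaching 10% at a null of 25% and 23% at 30%. MRI is also the only co-primary variable with no planned Month 6 between-arm difference and interval, although the data for one will exist.

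These figures assume 20 evaluable JointStem subjects and 10 controls, independent subjects, and the assumed rates shown. The gap in the text does not depend on those assumptions.

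**What to change.** 1. Add the proportion rated as improvement on MRI at Month 6 to the JointStem against positive control secondary endpoints (synopsis, Protocol 3.6.1, SAP 1.2.2). Add the JointStem minus control difference with an exact 95% CI to the analyses (synopsis, Protocol 6.1.5 item 3, SAP 6.2.3). Report it beside any cartilage statement. Do not make it a pass/fail test: at 20 against 10 the interval is about 60 to 75 points wide.
2. In Protocol 6.1.4 item 3 and SAP 6.1 item 3, report the JointStem count, denominator, percentage and exact 95% CI. Replace the conclusion that cartilage is improved with a statement that the observed percentage did or did not reach the 36% benchmark, with no attribution to JointStem over control on that basis. Name the analysis set that gives the deciding percentage.
3. Make the three-tests, gatekeeping and significance-level wording agree with this (synopsis, Protocol 3.6.1, 6.1.3 and 6.1.4; SAP 1.2.1, 6 and 6.1). Either call MRI a descriptive benchmark after two formal tests, or keep it as a formal test with a justified null rate and an exact one-sided 5% binomial test. Either choice cures the gap. If MRI's status changes, the synopsis co-primary list must change too.

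The cost is wording in the listed sections and one two-by-two estimate on data already collected, with no new visits, scans or subjects. The downside for the sponsor is a less favourable permitted MRI claim.
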